Evaluation of a Novel High-Resolution Diffusion-Weighted MRI Sequence

Study Intervention: High-resolution MRI

Funding Source: NIH

Amended version: 4/7/2020

Initial version: 1/8/2017

CONFIDENTIAL

This material is the property of Cedars-Sinai Medical Center. Do not disclose or use except as authorized in writing by the study sponsor.

Signature Page

The signature below constitutes the approval of this protocol and the attachments, and provides the necessary assurances that this trial will be conducted according to all stipulations of the protocol, including all statements regarding confidentiality, and according to local legal and regulatory requirements and applicable U.S. federal regulations and ICH guidelines.

Principal Investigator (PI) Name: _____

PI Signature: _____

Date: _____

CONFIDENTIAL

This material is the property of Cedars-Sinai Medical Center. Do not disclose or use except as authorized in writing by the study sponsor.

[figure not shown]
TABLE OF CONTENTS

| | |
|---|-----------|
| LIST OF ABBREVIATIONS | 1 |
| STUDY SCHEMA | 2 |
| STUDY SUMMARY..... | 2 |
| 1.0 STUDY ABSTRACT | 3 |
| 2.0 BACKGROUND AND RATIONALE | 4 |
| 3.0 STUDY DESIGN: | 5 |
| A. Overview..... | 5 |
| B. Study Population..... | 6 |
| C. Inclusion/Exclusion Criteria | 6 |
| D. Study endpoints | 6 |
| E. Study Design | 6 |
| F. Study Risks..... | 7 |
| G. Statistical Analysis | 9 |
| 4.0 REFERENCES..... | 10 |

LIST OF ABBREVIATIONS

| | |
|---------|--|
| ADC | Apparent diffusion coefficient |
| AS | Active surveillance |
| AUC | Area under the curve |
| DCE | Dynamic contrast enhanced |
| DWI | Diffusion-weighted imaging |
| EPI | Echo-planar imaging |
| hrMRI | High resolution MRI |
| mpMRI | Multiparametric MRI |
| MRI | Magnetic resonance imaging |
| PI-RADS | Prostate Imaging-Reporting and Data System |
| ROI | Region of interest |
| TRUS | Transrectal ultrasound |

STUDY SCHEMA

STUDY SUMMARY

| | |
|---------------------------------------|--|
| Title | Evaluation of a Novel High-Resolution MRI Sequence |
| Short Title | High resolution MRI |
| Protocol Number | |
| Phase | Not applicable |
| Methodology | Single arm, paired imaging |
| Study Duration | 3 years |
| Study Center(s) | Cedars Sinai Medical Center |
| Objectives | To determine if enhanced prostate imaging (high resolution MRI) will detect prostate lesions not seen on standard MRI. |
| Number of Subjects | 80 Study Subjects |
| Diagnosis and Main Inclusion Criteria | 
Inclusion Criteria:
 
 • Age over 18 years • Patients diagnosed with clinically localized prostate cancer • Low or Low-intermediate Risk Prostate cancer¹ defined as: 
 ◦ Pre-operative PSA \leq 20.0 ng/ml ◦ Clinical stage cT1 or cT2 ◦ Gleason score 3+3 or 3+4 • Patients choosing AS or already on AS as primary management strategy • No previous treatment for prostate cancer with radiotherapy, chemotherapy, or hormonal therapy • No contraindications for gadolinium enhanced MRI |
| Study Imaging | Standard multiparametric prostate MRI with high resolution diffusion weighted imaging |
| Control Imaging | Standard multiparametric prostate MRI |
| Reference standard | Evidence of disease progression on standard 12-core ultrasound-guided prostate biopsy. |
| Statistical analysis | 
Our hypothesis is that changes in tumor size or apparent diffusion coefficient (ADC) on high resolution MRI will predict presence of biopsy criteria for disease progression.
 
59 patients achieve 91% power to detect a 0.285 cm^3 difference (between patients progressing and patients not progressing) in the mean change in tumor volume at the two-sided two-sample t-test with a 0.05 level of significance. With respect to change in ADC, 59 patients achieve 80% power to detect a difference in the mean change ADC around 0.07 at the two-sided two-sample t-test with a 0.05 level of significance. This corresponds to about a 50% increase in ADC between the two groups of patients.
 |

1.0 STUDY ABSTRACT

We developed 3D magnetization-prepared high resolution diffusion weighted imaging (DWI) to overcome the major problems associated with 2D conventional single-shot echo-planar imaging (EPI) technique for prostate imaging. Major technical novelties are:

- Magnetization-prepared DWI was optimized to improve image quality. Standard DWI uses single-shot EPI acquisition, which inherently results in relatively poor image quality with apparent image artifacts, such as streaking (high image intensity bands) and geometric distortion (round objects may appear oval)², which may hinder the detection of small lesions. Magnetization-prepared DWI allows separate diffusion-preparation and data acquisition, which in turn allows segmented/multi-shot (vs single-shot) data acquisition and more robust acquisition techniques such as steady-state free precession (SSFP) or turbo-spin-echo (TSE) (vs EPI), which **eliminate typical image artifacts** associated with single-shot EPI.² An optimized **first-order motion-compensated diffusion preparation scheme** was developed to minimize the diffusion preparation time, which reduced T2 decay and minimize signal loss due to motion.
- 3D DWI was developed to achieve high and isotropic spatial resolution: While single-shot EPI acquisition is limited to 2D imaging with low in-plane resolution and thick slices (2.1x2.1x3.5 mm³), segmented/mult-shot SSFP or TSE acquisitions allow for contiguous slices of the entire prostate in one scan volume with isotropic resolution of 1.2x1.2x1.2 mm³, represents a **9-fold increase** over the conventional protocol. 3D DWI with high and isotropic spatial resolution is critically important for accurate measurement of lesion size and reducing partial voluming for **more accurate ADC quantification**.
- Hybrid Cartesian-radial readout and real-time-feedback self-gating **minimized the effects of motion**: Radial sampling was used to provide inherent motion robustness of images and allow for additional accelerated data acquisition through iterative non-Cartesian reconstruction. A self-gating signal was acquired to keep track of patient motion and data acquired during apparent motion was excluded from image reconstruction prospectively and the data was immediately reacquired.

This high resolution MRI (hrMRI), along with stand MRI (sMRI) will be obtained at baseline and again in approximately 1 year in patients on prostate cancer active surveillance. Changes in lesion size and ADC values will be assessed on the serial studies. This study evaluates the hypothesis that hrMRI will detect changes that sMRI cannot detect and that these changes will correlate with prostate cancer progression as determined on prostate biopsy.

2.0 BACKGROUND AND RATIONALE

Multiparametric MRI

Multiparametric MRI combining T2-weighted, diffusion-weighted, and dynamic contrast enhanced (DCE) images is commonly employed for detection and localization of prostate lesions.^{3, 4} Diffusion-weighted imaging (DWI) is sensitive to the diffusion of water molecules interacting with surrounding macromolecules. DWI, which provides a quantitative biological parameter called apparent diffusion coefficient (ADC) value, is a robust MRI parameter for differentiating benign and malignant prostate tissue.^{5, 6} In fact, the latest version of the Prostate Imaging-Reporting and Data System (PI-RADS) scoring system relies almost exclusively on DWI to identify tumors in the peripheral zone, which is where the vast majority of prostate cancers form. Findings on T2 images are not used to identify cancer, and DCE images are only used to differentiate between some PI-RADS 3 and 4 lesions. In a pilot study of prostate cancer AS, DW-MRI was useful for detecting progression of Gleason score based on changes in ADC value.⁷ Tumor size is another important clinical criterion for defining low risk prostate cancer, and tumor size based on DWI has been shown to crudely predict low risk prostate cancer.⁸ **However, conventional DWI using single-shot echo-planar imaging is unable to detect small tumors⁹, low grade tumors, or small changes in tumor size on serial imaging.** Approximately 20% of small, low grade tumors found in men on AS are detected on modern prostate MRI.¹⁰

High Resolution MRI

We introduce a new three-dimensional (3D) high-resolution diffusion-weighted imaging sequence (HR-DWI), which improves image quality while conferring at least a 5-fold improvement in resolution when compared to standard two-dimensional (2D) DWI (S-DWI). This novel 3D DWI technique has been developed by our team and can be applied on existing 1.5T or 3T MRI systems. S-DWI suffers from two important limitations. a) It uses single-shot echo-planar imaging (EPI) for data acquisition, which produces magnetic susceptibility induced streaking artifacts and geometric distortions so that round objects may appear oval. b) The relatively low signal-to-noise ratio and 2D image acquisition with S-DWI limit spatial resolution, which is defined by the minimum distance between two objects required to resolve them uniquely. Our HR-DWI overcomes these limitations by using magnetization prepared, multi-shot, turbo-spin-echo acquisition, which improves signal-to-noise ratio (SNR), spatial resolution, and image quality, and eliminates geometric distortions and streaking artifacts associated with EPI.

Preliminary studies

In preliminary studies assessing the performance of our HR-DWI in a prospective pilot trial of prostate cancer AS patients, the technique could detect tumors not seen on S-DWI and measure ADC, which correlates with grade.^{2, 11} This is important because the long-term natural history of small prostate cancers invisible to S-DWI has never been prospectively defined, in part due to lack of adequate imaging technology. In the era of molecular diagnostics and next-generation sequencing, an important step in understanding the biology of these lesions is to develop technologies to image and characterize these lesions. Importance of HR-DWI includes:

- Better imaging will allow these lesions to be monitored serially and **targeted for biopsy**, providing tissue for both histologic and molecular characterization.
- Higher resolution imaging will **better delineate tumor boundaries**, which can improve tumor staging and identify margins during partial-gland ablation by cryotherapy or high intensity focused ultrasound (HIFU), which was approved in 2015 by the U.S. FDA.

- Improved imaging resolution will allow for **more accurate measurement of tumor size and ADC, and detection of small changes in size or grade over time.** Standard prostate DWI has poor resolution; therefore, tumor growth kinetics have never been accepted as clinical criteria for cancer progression while on AS. If tumor growth kinetics or changes in grade determined by ADC prove prognostic, AS can rely less on serial transrectal biopsies, which can lead to serious complications.

Prostate Cancer

Prostate cancer is the most commonly diagnosed cancer among men and the second leading cause of cancer death in US men.¹² In the US, there are more than 200,000 newly diagnosed cases and nearly 40,000 deaths from prostate cancer annually. The lifetime risk of developing prostate cancer is one in seven men.¹³ The vast majority of men diagnosed with prostate cancer do not die of their disease even when curative therapy is not administered.^{14, 15} However, historically approximately 90% of men diagnosed with localized prostate cancer elect therapies such as radical prostatectomy or radiotherapy.¹⁶ The problem is that definitive therapies for prostate cancer can negatively impact quality-of-life by producing side-effects such as permanent urinary incontinence (7-14% post-treatment) and erectile dysfunction (44-51% post-treatment).¹⁷ Therefore overtreatment of prostate cancer has broad impact on quality of life and health care costs. The U.S. Preventive Services Task Force (USPSTF) recommends against PSA-based screening for all U.S. men; they argue that screening provides little to no benefit for most men while harming many men.¹⁸ On the other hand, the American Urologic Association (AUA) maintains that prostate cancer screening and risk assessment should be offered to asymptomatic men 55-69 years of age.¹⁹

Both opponents and advocates of PSA-based screening acknowledge that screening increases the detection of prostate cancer. An important assumption underlying the USPSTF recommendation against screening is that men with indolent cancer will continue to receive unnecessary treatment. An important assumption underlying the AUA recommendation for screening is that patients and physicians will be able to uncouple the diagnosis of prostate cancer from treatment. For example, men at highest risk for death from prostate cancer will receive treatment. All other men will undergo a period of active surveillance (AS). During followup on AS, men with evidence of high risk disease or cancer progression are offered definitive local therapy; however, men who continue to have low risk cancer can delay or completely avoid treatment. A barrier to AS is that clinical tools for risk-stratifying and monitoring men with newly diagnosed prostate cancer have limited accuracy. Prostate cancers are multifocal and biopsies are vulnerable to sampling error. Transrectal ultrasound-guided (TRUS) biopsy remains the gold standard for diagnosing prostate cancer and monitoring patients on AS. However, the standard prostate biopsy may miss clinically significant disease. TRUS biopsy understages the cancer in approximately a third of patients.^{20, 21} Furthermore, TRUS biopsy is accompanied by complications such as systemic infection, bleeding, and transient erectile dysfunction.²² **There is a clear need for innovations to reduce the clinical burden of diagnosing and monitoring prostate cancer.**

3.0 STUDY DESIGN:

A. Overview

Prostate cancer is the rare malignancy where there is no imaging strategy to serially monitor the tumor. MRI, which is the best tool we have for imaging the prostate, cannot detect most tumors and does not have the resolution to detect subtle changes in tumor size or tumor characteristic. Therefore, followup during AS relies on serial transrectal biopsies. An effective imaging strategy will decrease the clinical burden of AS. This prospective trial will compare the effectiveness of high resolution MRI (hrMRI) and standard MRI (sMRI) for serially monitoring prostate tumors for clinical progression, which is an indication for definitive local therapies such as radical prostatectomy and external beam radiotherapy. **We test the hypothesis that hrMRI may detect changes in tumor size or ADC value, which will predict clinical progression as defined by biopsy criteria.**

B. Study Population

The study population for recruitment will be patients at Cedars-Sinai Medical Center with prostate cancer on active surveillance.

C. Inclusion/Exclusion Criteria

Inclusion Criteria:

[figure not shown]
- Age over 18 years
- Patients diagnosed with clinically localized prostate cancer
- Low or Low-intermediate Risk Prostate cancer¹ defined as:
 - Pre-operative PSA \leq 20.0 ng/ml
 - Clinical stage cT1 or cT2
 - Gleason score 3+3 or 3+4
- Patients choosing AS or already on AS as primary management strategy
- No previous treatment for prostate cancer with radiotherapy, chemotherapy, or hormonal therapy
- No contraindications for gadolinium enhanced MRI

D. Study endpoints

Primary Endpoint: evidence of disease progression as defined by any of the following:

- Increase in Gleason score from 3 + 3 to Gleason sum 7 on biopsy
- Gleason score 4+3 on biopsy
- Gleason sum 8-10 on biopsy
- ≥ 3 Increase in number of positive cores
- Progression to nodal or bone involvement

E. Study Design

The study enrolls patients with low and low-intermediate risk prostate cancer. The National Comprehensive Cancer Network (NCCN) guidelines for prostate cancer list AS as an option for these patients.¹ There is no proven standard for monitoring patients on AS. The NCCN recommends a standard 12-core prostate biopsy every 1-2 years, at the discretion of the treating physicians depending on risk category and length of stable followup on AS. All Patients enrolling on the study will undergo standard (control) MRI (sMRI) and experimental High-Resolution MRI (hrMRI) at the time of study enrollment and again in 12 months (+/- 2 months). The patients then undergo a standard ultrasound guided 12-core prostate biopsy, where prostate ultrasound is used to sample 2 cores from the left and right lobes at the base, midgland and apex. At the discretion of the treating physician, the 2nd MRI and biopsy may be performed early if disease progression is suspected due to increasing PSA or adverse change in prostate exam. These for-cause MRI and biopsies will be used for the final analysis if the interval between MRIs is at least 5 months.

All MRI images will be read according to PI-RADS (version 2). All lesions with PI-RADS greater than or equal to 3 will be considered suspicious for cancer. A region of interest (ROI) application will be used. The circumference of a suspicious lesion will be drawn on each individual MRI slice. The lesion volume and average ADC will be calculated from the ROI's. At the discretion of the treating physician, the MRI images may be used to perform a MRI-ultrasound fusion biopsy of suspicious lesions, however, only the standard 12-core biopsy will be used for the statistical analysis.

Study calendar

| Study Calendar | |
|--------------------------------|--|
| Registration/consenting | |
| Standard and experimental MRI | |
| Standard and experimental MRI* | 12 months after first MRI (+/- 2 months) |
| Prostate biopsy* | within 3 months of the 2 nd MRI |

* At the discretion of the treating physician, the 2nd MRI and biopsy may be performed early if disease progression is suspected due to increasing PSA or adverse change in prostate exam.

F. Study Risks

All agents administered to patients in this study are approved by the U.S. Food and Drug Administration. This study investigates a novel software-based MRI imaging protocol that improves image resolution.

Magnetic Resonance Imaging (MRI)

MRI imaging is among the least invasive of all imaging modalities. The U.S. Food and Drug Administration has labeled MR systems of up to 4.0 Tesla as having “non-significant risk” and currently there is no evidence that MR imaging causes any long-term or irreversible effects in human beings. However, there are certain risks, which are detailed below.

MRI imaging utilizes magnetic fields and radiofrequency fields, both of which can be harmful in certain situations. Magnetic fields can cause ferromagnetic implants or ferromagnetic foreign bodies, such as intracranial aneurysm clips, shrapnel, and intraocular metal chips to become dislodged and tear the surrounding soft tissue. Therefore, MRI imaging is contraindicated in persons with ferromagnetic implants or ferromagnetic foreign bodies. It is also contraindicated in persons with electrically, magnetically or mechanically activated implants because the magnetic field can cause these to function erratically. In addition, persons wearing metallic objects may be at danger for them becoming dangerous projectiles, due to them inadvertently becoming introduced into the magnetic field. All subjects will be prescreened carefully and all scanners are used in accordance with guidelines set by the Bureau of Radiological Health.

Gadolinium contrast (Gadavist)

The intravenous contrast agent to be used in this study is gadolinium-based. The intravenous contrast has an excellent safety profile and is commonly used in MR studies. Allergic reactions are extremely rare, but may be more common in persons with a history of allergic reactions to iodinated contrast. Studies support a rate of serious allergy reactions of 1 in 20,000.

The most common side effect is bruising at the site of vein puncture, inflammation of the vein and infection; care will be taken to avoid these complications. Rare side effects are headache (5%), a coldness feeling on your arm where the needle was placed (2.8%), nausea (2.5%), dizziness (less than 2%), and vomiting (less than 1%). The use of gadolinium-based contrast agents in patients who already have serious kidney problems or who have a liver transplant may lead to a possibly fatal disease involving the skin, muscle and internal organs. This possibly fatal disease is called nephrogenic systemic fibrosis (NSF). Prior to giving a gadolinium-based contrast agent, we will ask about any history of kidney problems or liver transplant, and will test the health of the participant's kidneys by a blood test. If there are known risk factors for developing this disease, the participant will not be eligible to receive contrast.

Cedars Sinai conducted a research study looking for gadolinium deposits in the brain of 119 patients who underwent at least 7 contrast enhanced scans. Approximately half the patients had all their scans performed with a contrast agent categorized as a macrocyclic molecule and the remainder of the patients had all their scans performed with a contrast agent categorized as a linear agent. Patients who received the linear agent had contrast agents in their brain but none of the patients who received the macrocyclic agent had brain deposits. All patients in this study will receive the macrocyclic contrast agent for the MRI studies.

Hypersensitivity to Medications - Occasionally, people have allergic reactions when taking any medication. Subjects may receive medications such as contrast. Hypersensitivity reactions may include symptoms such as shortness of breath, wheezing,

flushing, nasal congestion and skin rash. In most cases, initial symptoms occur within minutes of drug administration and quickly reverse themselves or resolve with prompt medical treatment.

In general, allergic reactions to medicines are more likely to occur in people who have allergies to other drugs, foods, or things in the environment. Subjects will be asked about any pre-existing allergies before administering any medications during the study.

Incidental Findings

Only noted clinically significant incidental findings will be communicated to the subject, per CSMC IRB and Legal Department approved policy, as a result of agreeing to undergo a research MRI scan. No reports or images will be provided to subjects and their medical records.

G. Statistical Analysis

Power. The progression rate used for the power calculations comes from the REDEEM trial, which was a phase III trial conducted at 65 academic medical centers to assess the role of a 5-alpha reductase inhibitor to decrease progression during AS.²³ The REDEEM trial followed patient for a total of 3 years. In the placebo group, the progression rate for patients already on active surveillance undergoing their 2nd surveillance biopsy was 20%. This is expected to be a conservative estimate for progression since the REDEEM trial only included low risk patients while our study allows for low intermediate risk patients, who have a higher risk of progression. The patients at 20% risk for progression drive our power calculation.

Preliminary data from 13 patients with a total of 14 Gleason score 6 lesions show a mean of 0.19 cm³ and standard deviation of 0.19 cm³. We expect to detect at least a 50% increase in tumor volume in the group who progress compared to the group of patients that do not progress relative to baseline. Assuming that the standard deviation at the biopsy/MRI is similar to the baseline biopsy/MRI, group sample sizes of 12 patients who progressed and 47 patients that do not progress achieve 91% power to detect a difference in the mean change tumor volume around 0.285 cm³ at the two-sided two-sample t-test with a 0.05 level of significance. The estimate standard deviation of the difference in tumor size in each group (SDdiff) was estimated assuming the correlation coefficient measurements is 0. Since this correlation coefficient is likely to be positive, this power calculation is very conservative and much smaller mean change tumor volume can be detected. In fact, if this correlation coefficient equals to 0.6, then we can achieve 90% power to detect a mean change tumor volume around 0.18 cm³. With respect to change in ADC, preliminary data show that the mean and SD of ADC are 0.2 and 0.05, respectively. Under similar assumptions for the correlation coefficient between the first and second measurements (corr = 0), group sample sizes of 12 patients who progressed and 47 patients that do not progress achieve 80% power to detect a difference in the mean change ADC around 0.07 at the two-sided two-sample t-test with a 0.05 level of significance. This corresponds to about a 50% increase in ADC between the two groups of patients.

Multivariable logistic regression model will be used to study the association between change in tumor size and ADC from the first and the second biopsy as assessed by imaging and disease progression adjusting for potential baseline characteristics such as PSA level, clinical stage, NCCN risk category, and size of prostate nodule. Tumor size

and ADC is measured by averaging the volumes or ADCs of all detectable lesions (PI-RADS 3 - 5). Secondary analyses include studying this association by considering changes of single lesions. Automatic variable selection methods such as backward and stepwise selection will be used as a guideline to identify sets of important predictors of progression. More rigorous approach based on a 4-step procedure outlined in Collett²⁴ will be employed. Several model checking diagnostics will be employed to ensure that the logistic model is appropriate.²⁵

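### The plan declares a comparison of high-resolution with standard MRI and collects paired scans for it, but no endpoint or analysis makes that comparison

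*Combined protocol and SAP*

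**What the plan says.** Three places state a comparison.

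- Study Summary, Objectives (the only objective listed): "To determine if enhanced prostate imaging (high resolution MRI) will detect prostate lesions not seen on standard MRI".
- Section 1.0, Study Abstract: "This study evaluates the hypothesis that hrMRI will detect changes that sMRI cannot detect".
- Section 3.0 A, Overview: "This prospective trial will compare the effectiveness of high resolution MRI (hrMRI) and standard MRI (sMRI) for serially monitoring prostate tumors for clinical progression".

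The design could support it. The methodology is "Single arm, paired imaging", standard multiparametric MRI is named as control imaging, and Section 3.0 E schedules both scans for every man at enrollment and at 12 months. The same section treats lesions scored PI-RADS 3 or more as suspicious.

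The hypothesis put to the test is narrower. The Study Summary, under Statistical analysis, expects that "changes in tumor size or apparent diffusion coefficient (ADC) on high resolution MRI will predict presence of biopsy criteria for disease progression", and the bold sentence closing the Overview says much the same. Neither mentions sMRI.

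Section 3.0 D has one endpoint: "Primary Endpoint: evidence of disease progression as defined by any of the following". Section 3.0 G has t-test power for progressors against non-progressors, a logistic model of progression on change in size and ADC, and a single-lesion version of that association. It does not say which scan supplies the measurements.

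**The concern.** Progression is the same outcome whichever scan is used, so an endpoint of progression cannot by itself separate the modalities. A demonstrated association between change on hrMRI and progression is compatible with sMRI being worse, equal or better. If the plan is followed exactly, the sole listed objective goes unanswered.

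The stated comparisons also differ from one another. The objective is about lesion detection; the abstract and Overview are about serial change and progression. Each needs its own estimand. Without them, the unit of analysis, the men included and the handling of lesions seen on only one scan are all left to be chosen after the data are in hand, and those choices can decide which scan looks better.

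**Working it through.** **1. Is there a contrast anywhere?** Going through the plan item by item:

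| Item | Compares |
|---|---|
| Endpoint (3.0 D) | Nothing between scans |
| Power for volume and ADC (3.0 G) | Progressors with non-progressors |
| Logistic model (3.0 G) | Change in size and ADC with progression; modality not named |
| Secondary analysis (3.0 G) | Same association, by single lesion |

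There is no paired detection rate, no difference in AUC or sensitivity, and no power or precision for one. AUC is in the list of abbreviations but in no analysis.

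**2. What the stated power covers.** Inputs from Section 3.0 G: SD 0.19 cm³, correlation 0, groups of 12 and 47, difference 0.285 cm³, two-sided 0.05.

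- SD of change = 0.19 × √2 = 0.2687.
- Standard error = 0.2687 × √(1/12 + 1/47) = 0.2687 × 0.3234 = 0.0869.
- Noncentrality = 0.285 / 0.0869 = 3.28 on 57 df. Power is 89.7% by noncentral t and 90.7% by normal approximation, so the stated 91% reproduces.
- Section G speaks of at least a 50% increase in volume. Half of the 0.19 mean is 0.095 cm³. Noncentrality is then 0.095 / 0.0869 = 1.09 and power 19%.

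Both figures are for a t-test between patient groups. sMRI does not enter either.

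**3. What a yield estimate can deliver.** The denominator is the 80 planned men. The counts are assumed, because the documents give no discordance rates. Exact (Clopper-Pearson) 95% intervals for men with at least one hrMRI-only lesion:

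- 4/80 = 5.0% (1.4% to 12.3%)
- 10/80 = 12.5% (6.2% to 21.8%)
- 16/80 = 20.0% (11.9% to 30.4%)

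The study imaging is described as "Standard multiparametric prostate MRI with high resolution diffusion weighted imaging". If the hrMRI read includes the standard sequences, sMRI-only findings are near zero by construction. Exact McNemar then gives p = 2 × 0.5⁶ = 0.031 from six one-way men, so significance says little and the proportion is the useful summary.

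**4. What a monitoring contrast can deliver.** With d = 0.285 / 0.2687 = 1.06 and equal-variance normal change scores, AUC = Φ(d/√2) = 0.77; at 0.095 cm³ it is 0.60. The Hanley-McNeil standard error for 12/47 is 0.0851 at AUC 0.77 and 0.0954 at 0.60. The half-width for a paired difference is 1.96 × SE × √(2(1 − r)), where r is the assumed correlation between the two AUC estimates:

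| AUC | r = 0.3 | r = 0.5 | r = 0.7 |
|---|---|---|---|
| 0.77 | 0.197 | 0.167 | 0.129 |
| 0.60 | 0.221 | 0.187 | 0.145 |

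This supposes that all 59 men are measurable on both scans. If only half are (6/24, an assumption), the standard errors are 0.1212 and 0.1357 and the range widens to 0.18–0.31. Section 2.0 says "Approximately 20% of small, low grade tumors found in men on AS are detected on modern prostate MRI". That is a rate per tumor and does not convert to a proportion of men, but it warns that the subset measurable on sMRI may be small.

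**The case against.** The strongest reply is that the plan is coherent on its own terms: the hypothesis that it says it tests is hrMRI-only, and Section G fits that hypothesis. This stands. The core analysis is not misaligned with its tested hypothesis; the defect is that the objective, abstract and Overview promise more than is analysed.

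Three stronger readings are tempting, and the documents do not support them.

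- *That the planned model excludes sMRI altogether.* Section G names no modality; only the Study Summary and the bold Overview sentence point to hrMRI. Even if the model were fitted to each scan, two separate associations would not be a contrast.
- *That any later comparison would be post hoc.* The comparison is declared, the paired scans are scheduled, and a rule for a positive lesion is fixed. What is missing is the estimand and the method.
- *That the hrMRI test would succeed about 90% of the time.* That figure is t-test power at 0.285 cm³, whereas the planned analysis is a multivariable logistic model, and power is 19% at 0.095 cm³.

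It can also be said that a comparison in this sample is too imprecise to be worth specifying. The imprecision is real. It argues for an estimate with an interval rather than a test, and for fixing the method beforehand.

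**Conclusion.** The concern holds in this form: a comparison declared in three places, with paired data collected for it, has no endpoint, estimand or analysis. A positive planned result would support the hrMRI-only hypothesis and leave the sole listed objective open. This should be fixed; it does not invalidate the planned test.

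The conclusion itself comes from reading the sections side by side and needs no assumption. The size of what a comparison could show does rest on assumptions: the counts in the yield examples, the correlations of 0.3 to 0.7, the AUC range of 0.60 to 0.77, and the share of men measurable on both scans. On these, yield can be estimated usefully, while the AUC difference will be known only to within about 0.13 to 0.22 at best.

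**What to change.** Add to Section 3.0 G, before the data are analysed:

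1. **Main model.** State that it uses hrMRI measurements, in line with the Study Summary.
2. **Baseline yield, PI-RADS 3 or more.** Report the number of lesions seen on hrMRI but not sMRI, and the reverse. The main summary is the proportion of men with at least one hrMRI-only lesion, with an exact 95% CI. An any-lesion/no-lesion count alone would miss extra hrMRI lesions in men already positive on sMRI. Use McNemar only for that man-level classification, and only if sMRI-only findings are possible. Call the result yield, not accuracy, because only the standard 12-core biopsy is analysed. Where feasible, record the sMRI read before the high-resolution DWI is viewed.
3. **Monitoring.** Compute the same change measures from sMRI and report their association with progression beside hrMRI, with the paired difference (for example in AUC) and its CI, as an estimate only, in men measurable on both scans at both visits. Report separately the number of men, and of progressors, whose lesion is measurable on hrMRI only, since the subset cannot address lesions that sMRI does not see. If the subset holds only a few progressors, describe the changes without an AUC claim.
4. **Claims.** State that any claim of hrMRI advantage rests on items 2 and 3. Otherwise narrow the objective, abstract, Overview and conclusions to the hrMRI-only hypothesis.

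The cost is a paragraph, with no added scans or patients. If scans have already been read jointly, either state that as a limitation or re-read sMRI: 80 reads for baseline yield, up to 80 × 2 = 160 for both visits. The intervals will be wide. Narrowing the aims costs only text but gives up the comparison.
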